6.1.1. Neratinib Dose Adjustment

Neratinib dose adjustment and/or discontinuation and/or management of toxicity should be performed according to [Appendix 2](#) and [Section 10.1](#).

Recommended dose reductions for the -1 and -2 dose levels of neratinib are listed in [Table 3](#).

Table 3: Dose Reduction Levels for Neratinib-Related Toxicity

Dose Level	Neratinib
Recommended Starting Dose	240 mg
First dose reduction	200 mg
Second dose reduction	160 mg
Third dose reduction	120 mg

mg = milligrams

If doses of neratinib are held, study procedures for that cycle will proceed on schedule as planned, without any delay. Missed dose(s) of neratinib (i.e., any dose that is not administered within the protocol-defined administration window) will not be made up. **Note: Patients should take one dose per calendar day.** The dose adjustment guidelines represent the minimum set of measures the Investigator must follow. However, additional measures may be taken, as necessary, for certain patients per the Investigator's medical judgment. All dose modifications/adjustments should be documented in the patient's source file.

Once the neratinib dose has been reduced for a patient, all subsequent cycles must be administered at that dose, unless further dose reduction is required. Dose re-escalation will only be permitted if explicitly approved in advance by the Sponsor. Evidence of this approval must be contained within the patient's source file.

Patients must discontinue the investigational product if a criterion for withdrawal is met (see [Section 10.1](#)).

Reintroduction of the discontinued investigational product at a later time during the active treatment phase is not permitted.

Detailed rules for dose adjustments of neratinib in case of toxicity, including the dose levels to which the investigational product should be adjusted, are provided in [Appendix 2](#).

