10. PATIENT WITHDRAWAL AND REPLACEMENT

10.1. Investigational Product Discontinuation

Patients **must** be discontinued from **investigational product** under the following circumstances listed below and in [Appendix 2](#), unless otherwise agreed with the Medical Monitor:

- If the patient requires more than 2 dose reductions of neratinib (see [Appendix 2](#))
- If neratinib is withheld due to an SAEs for >28 days. Patients who are clinically benefiting from therapy with neratinib may be resumed on therapy after 28 days if approved in advance by the Sponsor
- Disease recurrence
- Initiation of alternative anti-cancer therapy. Any concurrent chemotherapy, radiotherapy (including palliative radiotherapy), surgery related to cancer, anticancer immunotherapy, or other anticancer treatments including other investigational agents (see [Section 7.3](#)).
- Pregnancy (see [Section 13.4](#))
- Investigator request
- Patient request (i.e., withdrawal of consent for treatment)
- AEs/toxicity

Withdrawal due to AE should be distinguished from withdrawal due to other causes, and recorded on the appropriate AE page of CRF. If a patient withdraws due to toxicity, even if discontinuation is not otherwise required per protocol guidelines, the withdrawal should be classified as withdrawal due to AE.

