Guidelines for dose adjustments of neratinib in the event of abnormalities in LVEF are shown in **Table A2.5**. LVEF assessments will be performed according to the Schedule of Procedures ([Appendix 1](#)). It is strongly recommended to use the same method of cardiac evaluation (ECHO or MUGA) at each time point for each patient.

Table A2.5: Left Ventricular Ejection Fraction (LVEF) Results Requiring Dose Adjustments of Neratinib

EVENT ON DAY OF SCHEDULED TREATMENT	Action
Asymptomatic absolute decline of LVEF $\geq 15\%$ from baseline OR absolute decline of LVEF $\geq 10\%$ ad below the lower limit of normal of 50%	
A) If LVEF is below 40%: hold neratinib and seek cardiology input OR continue neratinib with great caution.
 
Initiate monthly monitoring of LVEF
 
 • If while monitoring monthly, LVEF remains <40%: reconsider neratinib only if appropriate and after cardiology consult. • If while monitoring monthly, LVEF increases to $\geq 40\%$: continue neratinib, monitor LVEF every 12 weeks and consider cardiac support with input from cardiologist 
B) If LVEF is between 40% to 50%: continue neratinib with caution and surveillance.
 
Initiate monthly monitoring of LVEF.
 
 • If while monitoring, LVEF falls to <40%: Follow bullet point A instructions described above. • If while monitoring, LVEF remains $\geq 40\%$: continue neratinib, monitor LVEF every 12 weeks and consider cardiac support with input from cardiology.
Symptomatic cardiac failure	
 • Neratinib should be discontinued.

Abbreviations: LVEF: left ventricular ejection fraction.

If a patient has a second episode of asymptomatic decline in LVEF that meets either of the above criteria, permanently discontinue **neratinib**, repeat LVEF in 3-4 weeks and consider cardiology consult.

Note that, for AEs other than symptomatic LVEF decline, if **neratinib** is held for >28 days, the patient should be withdrawn from the active treatment phase of the study (see [Section 10.1](#)). In case of asymptomatic LVEF decline, patients may resume **neratinib** within 1 week after LVEF recovery is documented as above, even if the timeframe exceeds 3 weeks. If a site does not provide normal ranges for ECHO or MUGA, a lower limit of normal of 50% should be used.

Hematologic Toxicity

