Grade 1: Minimal skin changes or dermatitis (e.g., erythema, edema, or hyperkeratosis) without pain	
 • Continue neratinib and capecitabine at starting dose

NCI CTCAE v4.0	Action
Grade 2: Skin changes, e.g., peeling, blisters, edema, or hyperkeratosis, with pain, limiting instrumental ADL. PI: painful erythema and swelling of the hands and/or feet and/or discomfort affecting ADL.	
 Continue neratinib at starting dose level and hold capecitabine until recovery or to \leqgrade 1, then resume at starting dose. If the event recurs/persists, continue neratinib at starting dose level and reduce capecitabine dose to 1100 mg/m^2 (550 mg/m^2 BID)

Table A2.7: Hand and Foot Syndrome (Palmar-Plantar Erythrodysesthesia Syndrome) Requiring Dose Adjustment of Neratinib and Capecitabine (Continued)

NCI CTCAE v4.0	Action
Grade 3: Severe skin changes, e.g., peeling, blisters, edema, or hyperkeratosis, with pain, limiting self-care ADL. PI: moist desquamation, ulceration, blistering or severe pain of the hands and/or feet and/or severe discomfort limiting self-care ADL	
 Continue neratinib at starting dose level and hold capecitabine until recovery or to grade ≤ 1, then reduce dose to 1100 mg/m^2 (550 mg/m^2 BID) If the event recurs/persists, continue neratinib at starting dose level and capecitabine dose of 750 mg/m^2 (375 mg/m^2 BID)

Abbreviations: ADL: activities of daily living; BID: twice daily; NCI CTCAE v 4.0 National Cancer Institute Common Terminology Criteria for Adverse Events Version 4.0.

Pancreatitis

Guidelines for dose adjustments of neratinib and capecitabine for pancreatitis due to combination of neratinib plus capecitabine are show in [Table A2.8](#).

Table A2.8: Recommendations for Dose Adjustment of Neratinib and Capecitabine and Management of Patients with Pancreatitis

NCI CTCAE v.4.0	Action

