Grade 2 Pancreatitis: Enzyme elevation or radiologic findings OR Grade 3 Pancreatitis: Severe pain; vomiting; medical intervention indicated (e.g., analgesia, nutritional support)	
 Temporarily suspend (i.e., hold) neratinib and capecitabine Evaluate for any possible alternative causes If no alternative cause for pancreatitis is identified, discontinue neratinib and capecitabine permanently. If an alternative cause is identified (e.g., gallstones) or enzyme levels return to baseline within 3 weeks with clinical recovery, re-start treatment with reduced doses of neratinib 160 mg and capecitabine 1100 mg/m^2 (550 mg/m^2 BID). If the event occurs a second time, discontinue neratinib and capecitabine permanently.
Grade 4 Pancreatitis: Life-threatening consequences; urgent intervention indicated	
 Discontinue neratinib and capecitabine permanently.

Abbreviations: BID: twice daily; NCI CTCAE v 4.0 National Cancer Institute Common Terminology Criteria for Adverse Events Version 4.0

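### Table A2.8, read literally, tells one group of pancreatitis patients both to stop neratinib and capecitabine permanently and to restart them

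*Protocol*

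**What the plan says.** Protocol Appendix 2 introduces the table as "Guidelines for dose adjustments of neratinib and capecitabine for pancreatitis due to combination of neratinib plus capecitabine are show in" Table A2.8. The first row covers Grade 2 and Grade 3 together, and its lower entry point is "Grade 2 Pancreatitis: Enzyme elevation or radiologic findings". Both drugs are held and other causes are sought. Two rules follow:

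- **Stop:** "If no alternative cause for pancreatitis is identified, discontinue neratinib and capecitabine permanently".
- **Restart:** "If an alternative cause is identified (e.g., gallstones) or enzyme levels return to baseline within 3 weeks with clinical recovery, re-start treatment", at neratinib 160 mg and capecitabine 1100 mg/m² per day.

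Four other places bear on these rules:

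- **Section 6.1.1** gives the guidelines their status: "The dose adjustment guidelines represent the minimum set of measures the Investigator must follow". It also bars bringing back a discontinued investigational product during active treatment.
- **Section 6.3.1** refers capecitabine dose changes to the same appendix and to Section 10.1.
- **Section 10.1** makes the discontinuations listed there and in Appendix 2 mandatory "unless otherwise agreed with the Medical Monitor".
- **Table A1.2, footnote k** covers monitoring and imaging for pancreatitis. It does not address stopping or restarting.

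**The concern.** The two rules use different tests. The stop rule asks only whether another cause was found. The restart rule asks whether a cause was found or the patient recovered. They overlap in the patient who recovers without an explanation, and there they give opposite actions.

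That is also the patient in whom a drug cause is most plausible. A site that follows the restart rule re-exposes someone whom the preceding rule would stop. A site that follows the stop rule withdraws both anticancer drugs from a metastatic patient who has already had at least two HER2-directed regimens (inclusion criterion 5). Because the row is entered at Grade 2, a laboratory finding alone can raise the question.

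**Working it through.** The plan gives no figure to reproduce. The check is to apply both rules to every combination of the two conditions. Here *recovered* means enzymes at baseline within 3 weeks and clinically well.

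| Alternative cause found | Recovered | Stop rule applies | Restart rule applies | Result as written |
|---|---|---|---|---|
| No | No | Yes | No | Stop |
| No | Yes | Yes | Yes | **Stop and restart** |
| Yes | No | No | Yes, if *or* is literal | **Restart without recovery** |
| Yes | Yes | No | Yes | Restart |

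One of the four combinations conflicts on the literal reading. A second has a single instruction, but an implausible one: restart in a patient who is still unwell.

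**Can another reading remove the conflict?**

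1. *Apply the rules in order, stop first.* This gives one instruction. But the only patients whom the recovery condition adds to the restart rule are those with no cause found, and all of them have already been stopped. The recovery condition then does nothing.
2. *Treat recovery as an exception to the stop rule.* The stop rule states no exception and no waiting period. A negative work-up can be complete before 3 weeks have passed.
3. *Read* or *as* and. This removes the conflict and the restart without recovery, but it changes the text.

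**Existing hold limits.** Section 10.1 has a limit for SAEs: "If neratinib is withheld due to an SAEs for >28 days". A Grade 2 enzyme rise need not be an SAE. The note below Table A2.5 is broader and reaches ordinary AEs: if neratinib "is held for >28 days, the patient should be withdrawn from the active treatment phase of the study". Both texts concern neratinib; neither limits a capecitabine hold. The interval between the 3-week recovery window and this limit is 28 − 21 = 7 days. A rule that required both a cause and recovery within 3 weeks would leave a patient who recovers on days 22-28 with no way to restart, so the fix has to cover those days.

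**Expected number of cases.** The documents give no pancreatitis rate and no minimum number of metastatic patients. As an illustration only, assume a per-patient risk of 0.5% to 5% and that all 3-5 patients are metastatic:

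- low: 3 × 0.005 = 0.015 cases
- high: 5 × 0.05 = 0.25 cases

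These count all pancreatitis, so cases in the conflicting combination would be fewer. If no metastatic patient enrols, the number is 0.

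**The case against.** The case against has five parts.

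- **Sequential reading.** Taken in order, the rules give one answer, and Sections 6.1.1 and 10.1 lean toward stopping. A reader might infer from the table that the instructions clash on any reading; the documents do not support that. The clash is on the literal reading, and the sequential reading escapes it only by making the recovery condition idle.
- **Medical Monitor.** Section 10.1 lets the Medical Monitor agree an exception. That stands as a route for a single case. It does not tell a site that the rules conflict or which one governs, and the restart rule does not mention it.
- **Irreversibility.** A reader might infer that a stop can never be undone for either drug. The bar on reintroduction is in the neratinib section, and the capecitabine section does not repeat it. Section 10.1 also allows departures by agreement.
- **Intent.** Other rows of Appendix 2 allow restart on recovery without requiring another cause: Grade 2 and 3 general toxicities in Table A2.1, and Grade 3 ALT or bilirubin in Table A2.4 (recovery within 4 weeks). The sponsor may have meant the same here. This stands: the documents do not show which wording was intended.
- **Status.** The table is titled as recommendations. That does not help, because Section 6.1.1 makes the guidelines a floor that investigators must meet.

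**Conclusion.** The point holds as a minor wording error in a safety rule. On the literal text, one of four combinations receives incompatible instructions, and a second may restart before recovery. No other section resolves either.

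The scope is narrow: metastatic patients taking both drugs, after the second colonoscopy, when capecitabine begins (Section 6.3). The biopsy endpoint, the inflammatory markers and Cycle 1 diarrhea are all assessed before that, so a reader should not infer any effect on the trial's endpoints. The classification rests on the text alone. Only the illustrative case count uses an assumed risk.

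Stopping is the better default for unexplained cases because it agrees with Sections 10.1 and 6.1.1. That is a judgement about safety, not evidence of what the sponsor intended.

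**What to change.** At the next amendment, reword the Grade 2/3 row of Table A2.8:

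1. **No alternative cause, recovered or not:** discontinue both drugs, unless the Medical Monitor agrees otherwise under Section 10.1 while they are still on hold.
2. **Alternative cause identified and recovered** (enzymes at baseline and clinically well): restart at neratinib 160 mg and capecitabine 1100 mg/m².
3. **Alternative cause identified, recovery slower than 3 weeks:** keep both drugs on hold, and allow restart at the same reduced doses on recovery while the neratinib hold is within the 28-day limit in the note below Table A2.5. State that the capecitabine hold follows the same limit, since the present text covers neratinib only.

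Each of the four combinations then has one instruction. The third line closes the 7-day gap, so slow recovery adds no stop beyond the existing 28-day withdrawal.

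If the sponsor intended to rechallenge recovered, unexplained cases, it should instead limit the stop rule to patients with no alternative cause and no recovery within 3 weeks. The restart rule would still need to require recovery when a cause is found.

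**Cost:** a few lines in one appendix table, with no new data or procedures. The clinical downside of the recommended wording is real: recovered but unexplained cases, including Grade 2 enzyme rises, lose both drugs unless the Medical Monitor agrees otherwise.

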APPENDIX 3. EASTERN COOPERATIVE ONCOLOGY GROUP (ECOG) PERFORMANCE STATUS

Description	Grade
Fully active, able to carry on all pre-disease performance without restriction.	0
Restricted in physically strenuous activity, but ambulatory and able to carry out work of a light or sedentary nature, i.e., light house work, office work.	1
Ambulatory and capable of all self-care but unable to carry out any work activities. Up and about more than 50% of waking hours.	2
Capable of only limited self-care, confined to bed or chair more than 50% of waking hours.	3
Completely disabled. Cannot carry on any self-care. Totally confined to bed or chair.	4
Dead	5

APPENDIX 4. INHIBITORS AND INDUCERS OF THE CYTOCHROME P450 ISOENZYME

CYP3A4 Inducers		
Carbamazepine	Macrolide antibiotics	Rifabutin
Efavirenz	Phenobarbital	Rifampin
Glucocorticoids:	Phenylbutazone	Rifapentine
Dexamethasone	Phenytoin	St. John's Wort
Prednisone	Primidone	Sulfinpyrazone
CYP3A4 Inhibitors		
Amprenavir	Grapefruit juice	Paroxetine
Anastrozole	Indinavir	Propranolol
Cimetidine	Itraconazole	Quinidine
Clarithromycin	Ketoconazole	Quinine
Clotrimazole	Mibepradil	Ranitidine
Danazol	Miconazole	Ritonavir
Delavirdine	Mirtazapine (weak)	Saquinavir
Diethyldithiocarbamate	Nefazodone	Sertraline
Diltiazem	Nelfinavir	Sildenafil (weak)
Erythromycin	Nevirapine	Troglitazone
Fluconazole	Norfloxacin	Troleandomycin
Fluoxetine	Norfluoxetine	Zafirlukast
Fluvoxamine		
CYP3A5-7 Inducers		
Phenobarbital	Primidone	Rifampin
Phenytoin		

Source: [Tatro,2012.](#)

APPENDIX 5. SUBSTRATES AND INHIBITORS OF P-GLYCOPROTEIN (P-GP)

P-glycoprotein Substrates		
Amiodarone (eg, Cordarone)	Fluphenazine (eg, Prolixin)	Progesterone (eg, Prometrium)
Chlorpromazine (eg, Thorazine)	Hydrocortisone (eg, Cortef)	Promethazine (eg, Phenergan)
Clarithromycin (eg, Biaxin)	Indinavir (Crixivan)	Quinidine
Cyclosporine (eg, Neoral)	Itraconazole (eg, Sporanox)	Reserpine
Dactinomycin (Cosmegen)	Ketoconazole (eg, Nizoral)	Ritonavir (Norvir)
Daunorubicin (eg, Cerubidine)	Lidocaine (eg, Xylocaine)	Saquinavir (eg, Fortovase)
Dexamethasone (eg, Decadron)	Loperamide (eg, Imodium)	Sirolimus (Rapamune)
Digoxin (eg, Lanoxin)	Lovastatin (eg, Mevacor)	Tacrolimus (Prograf)
Diltiazem (eg, Cardizem)	Mifepristone (Mifeprex)	Tamoxifen (eg, Nolvadex)
Doxorubicin (eg, Adriamycin)	Mitoxantrone (Novantrone)	Teniposide (Vumon)
Erythromycin (eg, Ery-Tab)	Nelfinavir (Viracept)	Testosterone Delatestryl
Estradiol (eg, Estrace)	Nicardapine (eg, Cardene)	Trifluoperazine
Etoposide (eg, Vepesid)	Nifedipine (eg, Procardia)	Verapamil (eg, Calan)
Felodipine (Plendil)	Ondansetron (Zofran)	Vinblastine (eg, Velban)
Fexofenadine (Allegra)	Paclitaxel (eg, Taxol)	Vincristine (eg, Vincasar PFS)
P-glycoprotein Inhibitors		
Amiodarone (eg, Cordarone)	Indinavir (Crixivan)	Quinidine
Atorvastatin (Lipitor)	Itraconazole (eg, Sporanox)	Reserpine
Chlorpromazine (eg, Thorazine)	Ketoconazole (eg, Nizoral)	Ritonavir (Norvir)
Clarithromycin (eg, Biaxin)	Lidocaine (eg, Xylocaine)	Saquinavir (eg, Fortovase)
Cyclosporine (eg, Neoral)	Mifepristone (Mifeprex)	Tacrolimus (Prograf)
Diltiazem (eg, Cardizem)	Nelfinavir (Viracept)	Tamoxifen (eg, Nolvadex)
Erythromycin (eg, Ery-Tab)	Nicardipine (eg, Cardene)	Testosterone (Delatestryl)
Felodipine (Plendil)	Nifedipine (eg, Procardia)	Trifluoperazine
Fluphenazine (eg, Prolixin)	Progesterone (eg, Prometrium)	Verapamil (eg, Calan)
Hydrocortisone (eg, Cortef)	Propranolol (eg, Inderal)	

Source: [Tattro, 2012](#).

APPENDIX 6. DRUGS ASSOCIATED WITH RISK OF QT/QTC PROLONGATION LEADING TO TORSADE DE POINTES

Drugs Reported to Prolong QT Interval	
Analgesics	
Celecoxib (Celebrex)	Methadone (eg, Dolophine, Methadose)
Anesthetic agents	
Enflurane (eg, Ethrane)	Halothane
Isoflurane (eg, Forane)	
Antiarrhythmic agents	
Class IA	Class III
Disopyramide (eg, Norpace)*	Amiodarone (eg, Cordarone)* ^b
Procainamide (eg, Procanbid)*	Bretylium*
Quinidine*	Dofetilide (Tikosyn)* ^b
Class IC	Ibutilide (Corvert)* ^b
Flecainide (eg, Tambocor)* ^a	Sotalol (eg, Betapace)* ^b
Propafenone (eg, Rythmol)* ^b	
Anticonvulsants	
Felbamate (Felbatol)*	Fosphenytoin (Cerebyx)
Antiemetics	
Dolasetron (Anzemet) ^b	Droperidol (eg, Inapsine)* ^b
Ondansetron (Zofran)	
Antihistamines	
Desloratadine (Claritin) ^b (overdose)	Fexofenadine (Allegra)
Diphenhydramine (eg, Benadryl)	Hydroxyzine (Atarax)
Anti-infectives	
Amantadine (eg, Symmetrel)*	Macrolides and related antibiotics
Antimalarials	Azithromycin (eg, Zithromax)
Mefloquine (eg, Lariam) ^b	Clarithromycin (eg, Biaxin)* ^b
Quinine*	Erythromycin (eg, Ery-Tab, EES)* ^b
Antivirals	Telithromycin (Ketek) ^b
Efavirenz (Sustiva)*	Troleandomycin
Aazole antifungal agents	Pentamidine (eg, Pentam 300, Nebupent)*
Fluconazole (eg, Diflucan)* ^b	Quinolones
Itraconazole (eg, Sporanox)	Gatifloxacin (eg, Tequin)* ^b

Drugs Reported to Prolong QT Interval		
Ketoconazole (eg, Nizoral)		Levofloxacin (eg, Levaquin)* ^{a, b}
Voriconazole (Vfend) ^b		Moxifloxacin (eg, Avelox) ^b
Chloroquine (eg, Aralen)*		Oflloxacin (eg, Floxin)* ^b
Clindamycin (eg, Cleocin)		Sparfloxacin (Zagam) ^b
Foscarnet (Foscavir)		Trimethoprim/sulfamethoxazole (eg, Bactrim)*
Antineoplastics		
Arsenic trioxide (Trixenox)* ^b	Doxorubicin (eg, Adriamycin)	Tamoxifen (eg, Nolvadex)
Bronchodilators		
Albuterol (eg, Proventil) ^b	Salmeterol (Serevent) ^b	
Formoterol (Foradil) ^b	Terbutaline (eg, Brethine) ^b	
Isoproterenol (eg, Isuprel)		
Calcium channel blockers		
Isradipine (DynaCirc)	Nicardipine (eg, Cardene)	
Contrast media		
Ionic contrast media*	Non-ionic contrast media: Iohexol (Omnipaque)	
Corticosteroids		
Prednisolone (eg, Prelone)	Prednisone (eg, Deltasone)*	
Diuretics		
Furosemide (eg, Lasix)	Indapamide (eg, Lozol)	
Gastrointestinal agents		
Cisapride (Propulsid)* ^b	Famotidine (eg, Pepcid)*	
Immunosuppressants		
Tacrolimus (Protopic)* ^b (postmarketing)		
Miscellaneous		
Levomethadyl	Papaverine (eg, Pavadol three times daily [TID])*	
Moexipril/Hydrochlorothiazide (Uniretic)	Probucol (Lorelco)*	

1. PURPOSE OF ANALYSIS

The statistical analysis plan (SAP) outlines details of the statistical methods and analyses of the protocol **“An Open-Label Phase 2 Study to Characterize Colon Pathology in Patients With HER2 Amplified Breast Cancer Treated With Neratinib”** (PUMA-NER-6203), dated 04 September 2019.

The purpose of the SAP is to pre-specify analyses that are consistent with the protocol objectives to ensure appropriate interpretation of the data. It supplements the statistical section specified in the protocol with additional details and clarity related to the statistical analyses. The SAP must be finalized prior to database lock according to standard operating procedures. Deviations from this plan will be documented and described in the CSR.

2. PROTOCOL SUMMARY

2.1 Study Objectives

2.1.1 Primary Objective

The primary objective of this study is to characterize and understand colon pathogenesis related to neratinib-induced diarrhea through biopsies and images obtained by colonoscopy study

This objective will not be addressed by PUMA in this SAP.

2.1.2 Secondary Objectives

The secondary objectives of this study are:

- To characterize the incidence and severity of diarrhea during the first 28-day cycle.
- To analyze changes in serological and fecal inflammatory markers from baseline to second colonoscopy.

